##### Rate of reoperation due to the index hernia repair

The rate of subjects with a post procedure reoperation due to the index hernia repair will be presented by time intervals (post OP – 1 month, > 1 month – 3 months, > 3 months – 6 months, > 6 months – 12 months, > 12 months – 18 months, > 18 months – 24 months, > 24 months – 30 months, > 30 months – 36, > 36 months – 42 months, > 42 months – 48 months, > 48 months – 54 months, > 54 months – 60 months) and overall considering the time from post OP to end of study analogously to the primary variables (but without 95% CIs, no Kaplan-Meier analysis and no subgroup analysis except presentation by gender).

All reoperations documented on the reoperation page are counted as reoperations due to the index hernia repair. The date of reoperation will be used to calculate the time interval since date of surgery (day 0). In case of more than one reoperation per subject in an interval, the reoperations are counted only once per interval. A frequency table will present the reasons for reoperation.

##### Carolinus comfort scale™ (CCS)

The CCS is a 23-item questionnaire that measures sensation of mesh, severity of pain and movement limitations in the following eight domains: laying down, bending over, sitting up, activities of daily living, coughing or deep breathing, walking, stairs and exercise. The CCS is completed by the subjects at baseline and at all post procedure visits.

A total score will be calculated by summing up the scores of all 23 questions. Additionally, the total score by the three scales “sensation of mesh”, “pain” and “movement limitations” will be calculated by summing up the concerned questionnaire items (sensation of mesh: questions 1a, 2a, 3a, 4a, 5a, 6a, 7a, 8a; pain: questions 1b, 2b, 3b, 4b, 5b, 6b, 7b, 8b; movement limitations: 2c, 3c, 4c, 5c, 6c, 7c, 8c).

CCS will be analyzed in accordance to the CCS user guide. Computational algorithms including the handling of missing values are described in detail in the guideline. In summary, the following rules will be applied:

- ❑ Questions outcomes 0-5 will be used with lower scores indicating a more favorable health status.
- ❑ Not applicable or no response will be handled as missing values.
- ❑ Two or more outcomes ticked per question will be handled as missing value.
- ❑ If more than two questions are missing within any of the three scales (sensation of mesh, pain or movement limitations), the whole questionnaire will not be used. If less or equal to two questions are missing within any of the three scales (sensation of mesh, pain or movement limitations), the missing values will be replaced by the mean of the remaining items of the scale.

An exception of the rule is made for this study at baseline due to the fact that many values concerning sensation of mesh are “not applicable” at baseline (pre-operative assessment). For example, subjects without recurrent hernia cannot answer the questions related to sensation of mesh at baseline. Therefore, at baseline the scale scores for “pain” and “movement limitations” will be calculated for all subjects nevertheless, if within any of the two scales (“pain” or “movement limitations”) are less or equal to two questions missing applying the aforementioned rule (missing values will be replaced by the mean of the remaining items of the scale).

The total score and the three scales scores “sensation of mesh”, “pain” and “movement limitations” will be calculated and descriptive statistics will be reported by visit. At baseline the scale score “sensation of mesh” and the total score will be calculated for subjects with recurrent hernia and used mesh in situ and for subjects with recurrent hernia but unknown if previous mesh is still in situ (see listing 2.4 ‘Pre-operative diagnoses’ in Appendix A of the SAP). The absolute change from baseline will be calculated for the two scale scores “pain” and “movement limitations” and descriptively summarized by visit for all subjects. In case of sufficient entries for sensation of mesh at baseline, the absolute change from baseline will be calculated for the scale score “sensation of mesh” and the total score in the subset of subjects with recurrent hernia and used mesh in situ and with recurrent hernia but unknown if previous mesh is still in situ.

The outcome of the 23 individual questions will be tabulated by visit using both a frequency table and a table with basic statistics using the original answers of the subjects without replacement in case of missing values.

The calculated total score and the three scale scores of UVs and their change from baseline will be listed only.

#### SF-12® - 12 item short form health survey

The SF-12 is a multipurpose, 12-item health survey that measures eight domains of health: physical functioning, role limitations due to physical health (role-physical), bodily pain,

general health, vitality, social functioning, role limitations due to emotional problems (role-emotional), and mental health. It yields scale scores for each of these eight health domains, and two summary measures of physical and mental health: the physical component summary (PCS) and mental component summary (MCS). The SF-12 is completed by the subjects at baseline and at all post procedure visits.

The SF-12 domains and summary measures will be calculated using the QualityMetric Health Outcomes™ Scoring Software 4.5 applied to the SF-12v2 Health Survey using the 2009 U.S. general population t-scores. Missing score estimation (MSE) is included in the software.

The SF-12 domains and summary measures and their absolute change from baseline will be descriptively tabulated by visit. SF-12 domains and summary measures and their absolute changes from baseline will be calculated for UVs with performed SF-12 as well but will only be listed.

Surgical procedure time as measured from incision to closure (skin to skin)

The surgical procedure time (minutes) of the index procedure is calculated as time of skin closure complete minus time of first incision. Summary statistics will be presented for surgical procedure time.

Length of stay

The length of hospital stay (days) at index procedure is calculated as date of hospital discharge (index procedure, documented at Month 1 visit) minus date of hospital admission (documented at surgery (day 0)). The length of hospital stay will be descriptively tabulated.

**4.5 Safety Analysis**

Physical examination

The frequencies of changes in the physical examination since baseline will be shown for all post procedure visits (incl. unscheduled visit) using shift tables for the body systems “abdomen” and “skin”. The categories of the findings (normal/ abnormal) and the specification if abnormal (clinically significant/ not clinically significant) will be summarized for the shift tables in “normal”, “abnormal – NCS” and “abnormal – CS” with NCS = not clinically significant and CS = clinically significant.

The absolute change from baseline of body weight and BMI will be summarized descriptively.

Adverse events (AEs)

In this study, an AE is defined as any undesirable clinical event occurring in the abdominal space including the lower abdominal, inguinal and pubic regions (including the skin), as well as any other undesirable clinical events judged to be related to the study device or surgical procedure regardless of anatomical region.

AEs will be coded by using MedDRA version 16.1.

AEs will be tabulated by system organ class (SOC) and preferred term (PT) (MedDRA). The number of entries, as well as the number and rate of affected subjects will be reported.

Serious AEs (SAEs) and AEs with a causal relationship to the procedure (relationship to procedure is definitely related or possibly related; in case of a missing classification of the relationship to procedure a relation to the procedure is assumed), and AEs by severity are presented separately. A frequency table for procedure related AEs by time intervals (OP/

post OP – 1 month/ > 1 month – 3 months/ > 3 months – 6 months/ > 6 months – 12 months/ > 12 months – 18 months/ > 18 months – 24 months/ > 24 months – 30 months/ > 30 months – 36 months/ > 36 months – 42 months/ > 42 months – 48 months/ > 48 months – 54 months/ > 54 months – 60 months) presenting the number of events only will be displayed stratified by the subgroups ‘gender’ and ‘Surgical procedure performed’. Device related AEs are described in section 4.4.2 “Analysis of Secondary Variables” above.

A listing with high risk criteria (pre-study conditions) combined with AE information will be prepared additionally with the following variables: Total high risk criteria, What are the pre-study conditions the subject has, Total procedure related AEs, Total device related AEs, Total procedure related SAEs, Total device related SAEs and SAE term sorted by the total high risk criteria from high to low. Here AEs with causal relationship to procedure or device are displayed only.

Documented AEs of subjects who do not have Phasix™ Mesh implanted (subjects of ITT set but not included in the mITT set) will be listed separately.

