# 6.1.2 Enrollment

Subjects who sign an informed consent will be considered enrolled in this study. Subjects who provide consent for participation but do not meet all of the study eligibility criteria and do not receive the test device will be considered screen failures.

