# Version 4.0 October 30, 2017

#### **TABLE OF STUDY EVENTS** 6.4

Study Procedure	Screening and Baseline Period	Surgery	1 Month Visit	3 Month Visit	6 Month Visit	12 Month Visit	18 Month Visit	24 Month Visit	30 Month Visit 	36 Month Visit 
Visit Window (days)	Within 30 days of consent	0	30 + 7	90 + 30	180 + 30	365 + 30	545 + 30	730 + 30	910 + 30	1090 + 30
Describe study to potential subject	X									
Obtain informed consent	X									
Verify eligibility criteria	X	X 								
Collect demographics and medical history	X									
Conduct physical examination	Х		X	X	X	X	X	X		Х
Placement Procedure of Device		X 								
Surgical Pain Scale (VAS)	X		X	X	X	X	X	X		X
Carolinas Comfort Scale ®	X		X	X	X	X	X	X		X
SF-12 ®	X		X	X	X	X	X	X		Х
Collect adverse events/ complications		X	X	X	X	X	X	X	X	Х
Collect pain medication usage	X					X		X		X
Schedule next follow-up visit	X	X	X	X	X	X	X	X	X	

 Intraoperative verification of hernia size
 See Section 6.2 for surgical procedure details
 Investigator will determine whether clinic visit is necessary based on subject responses. Site will complete all study procedures at clinic visit.

Davol Inc. Phasix™ Mesh Protocol DVL-HE-011

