# 8 ADVERSE EVENTS

The Investigator is responsible for the detection and documentation of events meeting the criteria and definition of an AE or SAE, as provided in this protocol. All AEs that occur during the study should be treated with established standards of care that will protect the life and health of the study subjects.

AEs will be collected from the time of enrollment (AE onset after signing ICF) through the end of study participation (either study completion or early discontinuation) and will be documented in the medical record or source document and on study eCRFs. All events will be followed to satisfactory resolution or stabilization.

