#### 3.5 Assignment of Analysis Sets to Analysis

The mITT set will be considered the primary analysis. All analyses are based on the mITT set. In-/ exclusion criteria (where applicable with reason for failure to meet eligibility criteria), subjects per study site, applicable protocol version and demographics (listing only) will be presented for the ITT set. Adverse events of subjects in the ITT set but not in the mITT set

will be listed as well. The primary and secondary variables will additionally be analyzed using the PP set (including the subgroup analyses by gender but no further subgroup analyses).

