##### Device related adverse event incidence

Adverse events that are possibly or definitely related to device are considered. In case of a missing classification of the relationship to device a relation to the device is assumed. A frequency table will be prepared displaying the number of subjects and percentage of subjects with at least one event and number of events with event = device related AE.

Additionally, a frequency table grouped by Medical dictionary for regulatory activities (MedDRA) terms (system organ class (SOC) and preferred term (PT)) will be presented.

A frequency table for device related AEs by time intervals (OP/ post OP – 1 month/ > 1 month – 3 months/ > 3 months – 6 months/ > 6 months – 12 months/ > 12 months – 18 months/ > 18 months – 24 months/ > 24 months – 30 months/ > 30 months – 36 months/ > 36 months – 42 months/ > 42 months – 48 months/ > 48 months – 54 months/ > 54 months – 60 months) presenting the number of events only will be displayed stratified by the subgroups of ‘Surgical procedure performed’.

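### The overall AE, SAE and severity tables have no onset cut at surgery, so new events between consent and implantation count in the implanted subjects' rates (minor)

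*SAP*

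**What the plan says.** **Collection.** Protocol section 8: "AEs will be collected from the time of enrollment (AE onset after signing ICF) through the end of study participation". Enrolment is consent, not surgery; Protocol section 6.1.2: "Subjects who sign an informed consent will be considered enrolled in this study".

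**Definition.** SAP section 4.5 counts as an AE "any undesirable clinical event occurring in the abdominal space including the lower abdominal, inguinal and pubic regions (including the skin"), whether or not it is related to the mesh. Events elsewhere in the body count only if judged related to the device or the procedure.

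**Tabulation.** SAP section 4.5: "AEs will be tabulated by system organ class (SOC) and preferred term (PT) (MedDRA"), and "The number of entries, as well as the number and rate of affected subjects will be reported". SAEs, procedure-related AEs and AEs by severity are presented separately. Device-related AEs are in section 4.4.2.

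**Analysis set.** SAP section 3.5: "All analyses are based on the mITT set". Section 3.2 defines that set by implantation of the mesh. AEs of enrolled subjects who were not implanted are listed apart (section 4.5).

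**Missing causality.** SAP section 4.4.2: "In case of a missing classification of the relationship to device a relation to the device is assumed". Section 4.5 has the same rule for the procedure.

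**Time axis.** The SAP section 4 intervals start at Day 0, the date of surgery. The related-AE interval tables start at the operation. There is no pre-operative category.

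**The concern.** Being in the mITT set says which subjects are counted. It does not say which of their events are counted. With collection opening at consent and no onset rule in the tables, a new complication of the unrepaired hernia, or any other new abdominal event before surgery, enters the AE rate of a subject who is implanted afterwards. If it led to hospital admission, it also enters the SAE rate.

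Device safety is part of the stated objective (Protocol section 2), and readers will take an AE table for implanted subjects as experience after implantation. Events that preceded the mesh would be mixed into it without any sign in the table.

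The gap looks like an omission. SAP section 4.4.1 expressly limits recurrence and SSI to the time after surgery. The SAP also keeps AEs of non-implanted subjects out of the rates. An identical pre-operative event is thus listed or counted depending on whether the mesh was implanted later. SAP section 5, on changes from the protocol, does not mention the point.

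**Working it through.** The documents give no AE rate or count, so there is no planned figure to reproduce. The check has two parts.

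**1. Tracing one event.** Take an implanted subject with a new abdominal event after consent and before surgery.

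| Step | Rule | Result |
|---|---|---|
| Collected? | Protocol 8: onset after consent | Yes |
| An AE? | SAP 4.5: any abdominal event, related or not | Yes |
| Subject in the set? | SAP 3.2: mesh implanted | Yes |
| Excluded by onset from the overall AE, SAE or severity table? | SAP 4.5: no rule stated | No |
| In the device- or procedure-related tables? | SAP 4.4.2, 4.5: related, or relatedness missing | Only in those cases |
| In a time interval, if so? | SAP 4: intervals start at Day 0 | No |

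Interval tables exist only for device- and procedure-related AEs. An unrelated pre-operative event is in none of them and creates no mismatch.

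**2. Size.** Assumption: N = 120 implanted (the enrolment ceiling) or N = 110. A subject whose only AE was pre-operative adds 1/N to the proportion affected:

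- 1/120 = 0.83 percentage points
- 1/110 = 0.91 percentage points

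Illustration with N = 120 and assumed post-implant counts (exact 95% confidence intervals in brackets):

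| Subjects with a post-implant AE | With onset cut | +1 subject | +3 subjects | +6 subjects |
|---|---|---|---|---|
| 12 | 10.0% (5.3 to 16.8) | 10.8% | 12.5% | 15.0% |
| 36 | 30.0% (22.0 to 39.0) | 30.8% | 32.5% | 35.0% |

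Even six such subjects leave the estimate inside the confidence interval of the rate with the cut.

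*How many subjects?* The documents do not say, and the protocol sets no maximum time from consent to surgery. If a share q of 120 subjects has any pre-operative abdominal AE, the expected number is 120q and the chance of at least one is 1 − (1 − q)^120:

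| q (assumed) | Expected subjects | Chance of at least one |
|---|---|---|
| 0.5% | 0.6 | 45% |
| 1% | 1.2 | 70% |
| 2% | 2.4 | 91% |
| 5% | 6 | >99% |

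Only those with no later AE move the overall rate, so these are upper figures for that rate.

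A second rough scale: suppose 50 of 110 (45.5%) have an AE over 1,825 days at a constant rate, and the same rate applies before surgery. The daily rate is −ln(1 − 0.455)/1825 = 0.00033. The expected number with a pre-operative AE only is 110 × (1 − e^(−0.00033d)) × (1 − 0.455), where d is the wait in days:

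- d = 30: about 0.6 subjects
- d = 90: about 1.8 subjects

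Both scales point to at most a few subjects unless the wait is long or the pre-operative event rate is high.

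**The case against.** The strongest case on the other side is that the effect is slight and that the more serious consequences do not follow. Most of this stands.

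- **Device-related endpoint.** A reader might infer that pre-operative events will pass into this secondary endpoint. Protocol section 8.3 reserves the device category for events directly attributable to the device, which an event before implantation cannot be. The missing-relationship rule leaves a route, but Protocol section 8.5 requires the AE form to be completed in full and SAP section 4.8 requires queries to be resolved before closure. A blank would have to survive both.
- **Interval totals.** A reader might infer that they will disagree with the overall AE tables. That could arise only for the related-AE tables, and only through the same narrow route.
- **Hernia pain.** Pain already present at consent is not an AE, because onset must follow consent. Only new events matter.
- **Differences between sites.** The schedule row "Collect adverse events/ complications" in Protocol 6.4 has no mark at screening and starts at surgery. A reader might infer that sites differ in capture. However, recording at the surgery visit what happened since consent agrees with section 8, and Protocol section 6.1.3 requires AE collection from consent for screen failures. Differential capture is not shown.
- **Large inflation.** Going from 50/110 (45.5%) to between 53/110 (48.2%) and 58/110 (52.7%) needs 3 to 8 subjects with pre-operative AEs only. Nothing in the documents supports that number, and the constant-rate scale gives fewer.
- **Consequence.** Both primary endpoints are limited to after surgery, there is no hypothesis, and the analysis is descriptive.
- **Appendix A.** The table descriptions and footnotes are there. It was not available, so an onset filter may exist.

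None of this supplies an onset rule in the SAP text for the overall AE, SAE and severity tables. That gap remains.

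**Conclusion.** The point holds for the overall AE, SAE and severity tables. Applied as written, they count new events between consent and surgery in subjects later implanted. The bias in the overall AE and SAE rates can only be upward, because events are added over an unchanged denominator. It is probably small, at 0.8 to 0.9 percentage points per subject whose only AE was pre-operative, on the assumption of 120 to 110 implanted. The number of such subjects is unknown.

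The documents do not support a claim that the primary endpoints, or the device-related endpoint in any routine way, are distorted. This is a minor point, worth making because the correction is almost free. It rests on the SAP text alone and would fall if Appendix A already sets an onset filter.

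**What to change.** In SAP sections 4.4.2 and 4.5:

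1. Restrict the mITT tables of AEs, SAEs, AEs by severity, device-related AEs and procedure-related AEs to events with onset on or after the start of the index procedure (Day 0). State how partial onset dates and events dated Day 0 are assigned.
2. List mITT subjects' events from consent to surgery separately, as is already done for subjects not implanted.
3. State that the missing-relationship rule does not apply to those events.

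If Appendix A already contains such a filter, move the rule into the SAP text. As a clarification only, align the schedule in Protocol 6.4 with section 8 on when AE collection starts.

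The cost is a short SAP paragraph and one listing. AE start dates are already needed for the interval tables and for dating recurrence, so no new data are required.

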#### Device failure, malfunctions and defects

The investigator records if the surgical mesh device used in the study procedure failed to meet its performance specifications whether due to mechanical failure, malfunction or defects. Device failure, malfunctions or defects will be tabulated by the failure code.

#### Pain medication

All current pain medication is captured at baseline. Hernia associated pain medication is captured at 12, 24, 36, 48 and 60 months. All documented pain medication will be coded by world health organization drug dictionary (WHO-DD) and will be tabulated by anatomical therapeutic chemical classification (ATC) level 1, level 4 and WHO-DD preferred term.

A frequency table by Month 1, Month 3, Month 6, Month 18, Month 30, Month 42 and Month 54 visit (Month 30, 42 and 54 only if clinic visits were performed) will be presented showing the intake of prescription or OTC medications for treatment of pain related to hernia repair (yes/no) including the classification in “non-narcotic” and “narcotic” if “yes”.

### **4.6 Analysis of Other Relevant Variables**

#### Protocol deviations

The proportion of subjects with any protocol deviation will be tabulated.

### **4.7 Missing Values**

No missing value imputation methods will be applied. For handling of missing values in the quality of life assessments (CCS and SF-12®) see section 4.4.2.

### **4.8 Data Base Closure and Data Review**

A data base closure will be performed prior to the analysis. All parameters will be checked, as specified in the data validation plan, and all queries resolved before data base closure and analysis.

A data review will be conducted prior to data base closure to check for protocol deviations and to allocate the subjects to the analysis sets. At least the following items will be discussed:

- Informed consent form signed (date subject signed informed consent is documented)
- Phasix™ Mesh implantation
- Any violation of inclusion/exclusion criteria
- Subjects for which the index hernia repair/ Phasix™ Mesh was cut through or a piece of the Phasix™ Mesh was removed during a surgery not related to the index hernia repair (for example documented as other action taken on the AE form)
- Reasons for premature discontinuation
- Protocol deviations as captured in the eCRF on the protocol deviation log page

If required, critical data/ analysis issues can additionally be discussed (e.g. review reasons for reoperations, SSIs and hernia recurrences).

These evaluations and assessments will be done together and in agreement with the Sponsor, however FGK will provide the Sponsor with the appropriate subject listings (as defined in Appendix A to the SAP). Data review can be done via a telephone conference or in writing.

After data review minutes (including the affiliation of subjects to the ITT, mITT and the PP set) have been signed by both the Sponsor and FGK, data base closure will be performed.

